7.1.2 Serious Adverse Event Definition

Serious AE (SAE) means any untoward medical occurrence that at any dose:

- Results in **death**.
- Is **life-threatening** (refers to an AE in which the patient was at risk of death at the time of the event. It does not refer to an event which hypothetically might have caused death if it were more severe).
- Requires inpatient **hospitalization or prolongation of an existing hospitalization** (see clarification in the paragraph below on planned hospitalizations).
- Results in **persistent or significant disability or incapacity**. (Disability is defined as a substantial disruption of a person's ability to conduct normal life functions).
- Is a **congenital anomaly/birth defect**.
- Is a **medically important event**. This refers to an AE that may not result in death, be immediately life threatening, or require hospitalization, but may be considered serious when, based on appropriate medical judgment, may jeopardize the patient, require medical or surgical intervention to prevent 1 of the outcomes listed above, or involves suspected transmission via a medicinal product of an infectious agent. Examples of such medical events include allergic bronchospasm requiring intensive treatment in an emergency room or at home, blood dyscrasias or convulsions that do not result in inpatient hospitalization, or the development of drug dependency or drug abuse; any organism, virus, or infectious particle (eg, prion protein transmitting Transmissible Spongiform Encephalopathy), pathogenic or nonpathogenic, is considered an infectious agent.

Clarification should be made between a serious AE (SAE) and an AE that is considered severe in intensity (Grade 3 or 4), because the terms serious and severe are NOT synonymous. The general term *severe* is often used to describe the intensity (severity) of a specific event; the event itself, however, may be of relatively minor medical significance (such as a Grade 3 headache). This is NOT the same as *serious*, which is based on patient/event outcome or action criteria described above, and is usually associated with events that pose a threat to a patient's life or ability to function. A severe AE (Grade 3 or 4) does not necessarily need to be considered serious. For example, a white blood cell count of 1000/mm³ to less than 2000 is considered Grade 3 (severe) but may not be considered serious. Seriousness (not intensity) serves as a guide for defining regulatory reporting obligations.

7.1.3 Severity Rating

The investigator will evaluate the severity of each adverse event. NCI Common Terminology Criteria for Adverse Events (CTCAE v.4.0) or study specific toxicity tables provided in the protocol define severity. If not included in CTCAE v.4.0, severity is expressed in numerical grade using the following definitions:

Grade 1: Mild-asymptomatic or mild symptoms; clinical or diagnostic observations only; intervention not indicated.

Grade 2: Moderate-minimal, local or noninvasive intervention indicated; limiting age appropriate instrumental ADL.

Grade 3: Severe-severe or medically significant but not immediately life-threatening; hospitalization or prolongation of hospitalization indicated; disabling; limiting self care ADL.

Grade 4: Life-threatening consequences; urgent intervention indicated.

Grade 5: Death related to AE

Attribution/Relationship to study drug:

Definite – clearly related

Probable – likely related

Possible – may be related

Unlikely – doubtfully related

Unrelated – clearly not related

7.1.4 Expectedness

An Expected Adverse Event is one where the specificity or severity is consistent with the current information available from the resources.

An Unexpected Adverse Event is one where the nature, severity, or frequency of the event is related to participation in the research is not consistent with either:

1. The known or foreseeable risk of adverse events associated with the procedures involved in the research that are described in (a) the protocol-related documents, such as the IRB-approved research protocol, any applicable investigator brochure, and the current IRB-approved informed consent document, and (b) other relevant sources of information, such as product labeling and package inserts: or
2. The expected natural progression of any underlying disease, disorder, or condition of the subject (s) experiencing the adverse event and the subjects(s) predisposing risk factor profile for the adverse event.

(OHRP Guidance on reviewing unanticipated problems 2007)

7.2 Procedures for Reporting Serious Adverse Events

AEs may be spontaneously reported by the patient and/or in response to an open question from study personnel or revealed by observation, physical examination, or other diagnostic procedures. Any clinically relevant deterioration in laboratory assessments or other clinical finding is considered an AE. When possible, signs and symptoms indicating a common underlying pathology should be noted as one comprehensive event. For serious AEs, the investigator must determine both the intensity of the event and the relationship of the event to study drug administration. For serious pretreatment events, the investigator must determine both the intensity of the event and the relationship of the event to study procedures.

AEs which are serious must be reported to Millennium Pharmacovigilance (or designee) from the date the participant signs Informed Consent through 30 days after administration of the last dose of Ixazomib. Any SAE that occurs at any time after completion of Ixazomib treatment or after the designated follow-up period that the sponsor-investigator and/or sub-investigator considers to be related to any study drug must be reported to Millennium Pharmacovigilance (or designee). In addition, new primary malignancies that occur during the follow-up periods must be reported, regardless of causality to study regimen, for a minimum of three years after the last dose of the investigational product, starting from the first dose of study drug. All new cases of primary malignancy must be reported to Millennium Pharmacovigilance (or designee).

Planned hospital admissions or surgical procedures for an illness or disease that existed before the patient was enrolled in the trial are not to be considered AEs unless the condition deteriorated in an unexpected manner during the trial (e.g., surgery was performed earlier or later than planned). All SAEs should be monitored until they are resolved or are clearly determined to be due to a patient's stable or chronic condition or intercurrent illness(es).

7.2.1 Site reporting responsibilities:

Since this is an investigator-initiated study, the principal investigator [name], also referred to as the sponsor-investigator, is responsible for reporting serious adverse events (SAEs) to any regulatory agency and to the sponsor- investigator's EC or IRB.

Regardless of expectedness or causality, all SAEs (including serious pretreatment events) must also be reported to Millennium Pharmacovigilance:

Fatal and Life Threatening SAEs within 24 hours of the sponsor-investigator's observation or awareness of the event

All other serious (non-fatal/non life threatening) events within 4 calendar days of the sponsor-investigator's observation or awareness of the event

See below for contact information for the reporting of SAEs to Millennium Pharmacovigilance.

The sponsor-investigator must fax the SAE Form per the timelines above.

The SAE report must include at minimum:

- **Event term(s)**
- **Serious criteria**
- **Intensity of the event(s):** Sponsor-investigator's or sub-investigator's determination. Intensity for each SAE, including any lab abnormalities, will be determined by using the NCI CTCAE version specified in the protocol, as a guideline, whenever possible. The criteria are available online at <http://ctep.cancer.gov/reporting/ctc.html>.
- **Causality of the event(s):** Sponsor-investigator's or sub-investigator's determination of the relationship of the event(s) to study drug administration.

Follow-up information on the SAE may be requested by Millennium.

Intensity for each SAE, including any lab abnormalities, will be determined by using the NCI CTCAE version used at your institution, as a guideline, whenever possible. The criteria are available online at <http://ctep.cancer.gov/reporting/ctc.html>.

In the event that this is a multisite study, the sponsor-investigator is responsible to ensure that the SAE reports are sent to Millennium Pharmacovigilance (or designee) from all sites participating in the study. Sub-investigators must report all SAEs to the sponsor-investigator so that the sponsor-investigator can meet his/her foregoing reporting obligations to the required regulatory agencies and to Millennium Pharmacovigilance, unless otherwise agreed between the sponsor-investigator and sub-investigator(s).

Relationship to all study drugs for each SAE will be determined by the investigator or sub-investigator by responding yes or no to the question: Is there a reasonable possibility that the AE is associated with the study drug(s)?

Sponsor-investigator must also provide Millennium Pharmacovigilance with a copy of all communications with applicable regulatory authorities related to the study or study drug(s), including, but not limited to, telephone conversation logs within 24 hours but no later than 4 calendar days of such communication.

SAE and Pregnancy Reporting Contact Information

SAE and Pregnancy Reporting Contact Information

[contact]
Email: [contact]

Reporting Form:

- US FDA MedWatch 3500A:
<http://www.fda.gov/Safety/MedWatch/HowToReport/DownloadForms/default.htm>

1. The investigator/ site is responsible to report all SAEs to the Study Monitor within 24 hours of becoming aware of the event. A written report must follow within 48 hours.
2. Each investigator is responsible to report all AEs/SAEs to their local IRB following guidelines set by that IRB. The FCCC ERP reserves the right to request an event be reported to the IRB at their discretion. Copies of events reviewed by the IRB must be sent via fax to the ERP Regulatory Coordinator at [contact]
3. Any investigator who is in doubt of whether a particular AE needs to be reported is directed to call the Study Monitor for confirmation with the Principal Investigator
4. If the results of an investigator or ERP investigation show an adverse event not initially determined to be reportable is so reportable, the investigator will report the event following the above guidelines based on the date the determination is made.
5. Copies of all related correspondence and reporting documents must be submitted to the ERP Regulatory Coordinator and will be maintained in a regulatory file.

The participating site should report events to:

Study Monitor
Fox Chase Cancer Center
Clinical Trials Operations
[name]
[name]
[contact]
[contact]

7.2.2 ERP Reporting Responsibilities:

1. Adverse events which meet all of the following criteria must be reported to all participating institutions for IRB submission within 2 weeks of notification of the event.
 - i. Unexpected (in terms of nature, severity, or frequency) given (a) the research procedures that are described in the protocol-related documents, such as the IRB-approved research protocol and informed consent document; and (b) the characteristics of the subject population being studied;
 - ii. Possibly related to participation in the research (possibly related means there is a reasonable possibility that the incident, experience, or outcome may have been caused by the procedures involved in the research); and
 - iii. Serious (refer to above definition) or otherwise one that suggests that the research places subjects or others at a greater risk of physical or psychological harm than was previously known or recognized.
2. If the adverse event requires modification of the study protocol and informed consent, these changes will be provided to all participating institutions in the form of an amendment from the ERP for each site's IRB of record along with the report of the adverse event.
3. Copies of all related correspondence and reporting documents will be maintained in a centralized regulatory file for this study by the ERP.
4. SAEs that are related, unexpected, fatal, or life-threatening are reportable through the Food and Drug Administration (FDA) MedWatch program by telephone or fax no later than 7 calendar days after initial receipt of the information. Further information on the timing of submissions is as directed by FDA guidelines (www.fda.gov/medwatch/index.html). Serious, unexpected events that suggest significant clinical risk will be submitted to within 15 calendar days after initial receipt of this information.

Food and Drug Administration:
Telephone [name]
Fax [name]
<http://www.fda.gov/medwatch/report.htm>

Mandatory Drug Reporting:
Central Document Room
Center for Drug Evaluation and Research
Food and Drug Administration
[name]
[name]
Office of Post-Marketing Drug Risk Assessment (HFD 730)
Center for Drug Evaluation and Research
Food and Drug Administration
[name]
[name]

[contact] for any further questions regarding where to send drug mandatory reporting forms

7.3 Procedures for Reporting Drug Exposure During Pregnancy and Birth Events

If a woman becomes pregnant or suspects that she is pregnant while participating in this study or within 90 days after the last dose, she must inform the investigator immediately and permanently discontinue study drug. The sponsor-investigator must immediately fax a completed Pregnancy Form to the Millennium Department of Pharmacovigilance or designee. The pregnancy must be followed for the final pregnancy outcome.

If a female partner of a male patient becomes pregnant during the male patient's participation in this study, the sponsor-investigator must also immediately fax a completed Pregnancy Form to the Millennium Department of Pharmacovigilance or designee. Every effort should be made to follow the pregnancy for the final pregnancy outcome.

[figure not shown]
Pregnancy Reporting Form:

- Pregnancy Report Form (a sample is provided by Millennium)

8 STATISTICAL AND QUANTITATIVE ANALYSES

8.1 Statistical Methods

Figure 8-1: Flow diagram of statistical design for the phase II of the study

8.1.1 Definition of Phase II and exploratory endpoints and Analytic Plan

The phase II dose will be determined by an initial standard '3+3' phase I component as described in Section 4.1. Once a RP2D is reached, the phase II will begin.

Definition of phase II primary endpoint: Progression free survival at 8 and 16 weeks using RECIST v 1.1, defined from date of treatment initiation to date of progression according to RECIST or death, or is censored at the date of the last imaging. If patient is not evaluated at 8 and/or 16 weeks then the patient is not considered as alive and progression-free.

Definition of secondary outcomes/endpoints:

1. Composite of unacceptable toxicity at 8 weeks (grade 4 non-hematologic toxicity thought to be definitely, probably or possibly related to study drug)
2. Overall response using RECIST v1.1.

Definition of exploratory objectives:

1. Changes in STAT1 phosphorylation and MHC1 up regulation in PBMCs from baseline to week 2, 3, 7, EOT.
2. Degree of desmoplasia in archived FFPE tumor samples and change in serum IL-6
3. Degree of nuclear NF- κ B p65 and STAT1 in archived FFPE tumor samples

Analytic plan for primary and secondary objectives:

Kaplan Meier curves will be used to estimate the distribution of progression free survival, median survival, and 1-year survival. Proportions, 95% confidence intervals, will be used to characterize composite rate of unacceptable toxicity and overall response rate. All analyses are for estimation only, and no larger inference will be generated given the sample size of the study.

Analytic plan for exploratory objectives:

Pre- and post- treatment phosphorylation changes in pSTAT1 and MHC1 (flow data, the MFIs will be log10) and serum IL-6 will be analyzed by paired t-tests. Degree of desmoplasia and nuclear NF- κ B and STAT1 will be quantified using standard immunohistochemical methods. Statistical analysis for western blots and responders vs non-responders tumor immunohistochemistry will be performed using non-parametric Mann-Whitney test and/or paired t-tests.

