3. STUDY ENDPOINTS

Phase I Primary Endpoint

1. Presence or absence of dose-limiting toxicity during one cycle of pegylated interferon alpha with ixazomib.

Phase II Primary Endpoint

1. Progression free survival at 8 and 16 weeks using RECIST v 1.1.

Phase II Secondary Endpoints

1. Unacceptable toxicity rate at 8 weeks (any grade 5 toxicity, grade 4 neuropsychiatric toxicity or grade 4 clinically significant non-hematologic toxicity thought to be definitely, probably or possibly related to study drug)

2. Overall response rate at 8 and 16 weeks using RECIST v1.1.

[figure not shown]
Exploratory Endpoints for Phase I and II

1. To examine changes in STAT1 phosphorylation and MHC1 up regulation in PBMCs as an indicator of IFN activity
2. To use archived FFPE tumor tissue to correlate activated tissue stroma (i.e., desmoplasia) with IL-6 and patient outcomes
3. To use archived FFPE from past biopsies for IHC analysis of nuclear NF-κB p65 and STAT1.

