8.1.2 Sample Size Determination

The design incorporates two conditions not usually treated. First, the final group of patients in the phase I component is considered part of the phase II trial. Second, the phase II part has two end-points, toxicity (UT: unacceptable toxicity) and efficacy. The relation between toxicity and efficacy is explicitly taken into account. We test the composite null hypothesis:

$H_0: p(UT) > 0.25 \text{ or } p(PFS > 8 \text{ weeks}) < 0.5 \text{ or } p(PFS > 16 \text{ weeks}) < 0.35$

versus the alternative:

$H_1: p(UT) < 0.05 \text{ and } p(PFS > 8 \text{ weeks}) > 0.66 \text{ and } p(PFS > 16 \text{ weeks}) > 0.56.$

Eleven new patients will be treated in the first stage of the phase 2 component. If 3/17 patients have UTs OR if at most 8/17 are alive and PF at 8 weeks the trial will be either be

suspended for excess toxicity or for futility. The decision for early termination (or amendment) is based on these cut points. If either 3 of 17 stage I patients are DLTs OR if at most 8 of 17 are PF at 8 weeks then terminate or hold up. The final decision point, PFS at 16 weeks is not relevant; the number of such patients does not influence the early decision. The confusion seems to relate to the alternative hypothesis which is couched in terms of 'AND'. It does, of course, require both early and late components of the outcome to be defined. Finally, although 3/17 is less than 0.25, this is the cut point, clearly between 0.05 and 0.25. The early PFS cut point 8/17 is less than 0.5 but is only a cut point.

At that point we will consider protocol amendment. Otherwise, 17 new patients will be recruited. If at least 14/34 patients are PF at 16 weeks AND less than 4/34 have UTs the null hypothesis will be rejected and the treatment declared efficacious. Otherwise it will be declared either too toxic or not efficacious.

Further operating characteristics and statistical details can be found in Appendix 12.3

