12.3 Statistical Considerations and Operating Characteristics for Phase II

Operating characteristics of the design depend on four conditions: toxicity being low (0.05) or high (0.25) and PFS at 16 weeks being low (0.35) or high (0.56). They are summarized below:

1. Toxicity = 0.05 and PFS = 0.56. In this case the power of the study is at least 80%. The chance of early stopping (in error) for excess toxicity is less than 1%. The chance for stopping (in error) for futility varies from 8% to 12% depending on the relation of toxicity to PFS (see details below).
2. Toxicity = 0.05, PFS = 0.35. The chance of early stopping for futility varies from 49% to 57%. The chance of declaring treatment efficacious (type I error) varies from 10% to 21%.
3. Toxicity = 0.25 and PFS = 0.35. Type I error varies from less than 1% to about 5%. Chance of stopping early for either excess toxicity or futility varies from about 26% to about 59%.
4. Toxicity = 0.25 and PFS = 0.56. Type I error varies from about 5% to about 10%. Chance of early stopping for excess toxicity is about 27%.

The term 'UT' here means severe toxicity for which, if frequent enough, dictates dose reduction or trial termination. This early stopping design is an extension of the method of Litwin, Wong and Hudes (Statistics in Medicine, 2007,26:4400-4415). Below, the chance that a patient has a UT and also is PF at 16 weeks is represented by 'a'. 'b', 'c' and 'd', similarly, represent the indicated joint probabilities.

Let $p = p(\text{PFS} > 16 \text{ weeks})$, $p_1 = p(\text{PFS} > 8 \text{ weeks})$ and $p_2 = p(\text{PFS} > 16 \text{ weeks} | \text{PFS} > 8 \text{ weeks})$. Also, let $\text{ptox} = p(\text{UT in 16 weeks})$. Let $\text{ptox1} = f^* \text{ptox} = p(\text{UT in initial 8 week period})$ and $\text{ptox2} = (1-f)^* \text{ptox} = p(\text{UT in 8 through 16 week period} | \text{no UT in the initial 8 weeks})$. Then, $b = p - a$, $c = \text{ptox} - a$ and $d = 1 - a - b - c$. a_1, b_1, c_1 , and d_1 are similarly determined from p_1 and ptox1 . a_2, b_2, c_2 and d_2 are determined likewise, from p_2 and ptox2 .

The table:

$P(\text{UT})$	$1 - p(\text{UT})$	
a	b	$p(\text{PFS} > 16 \text{ weeks}) = 0.56$ (under the alternative hypothesis)
c	d	$p(\text{PFS} < 16 \text{ weeks}) = 0.44$
ptox	$1 - \text{ptox}$	1 ($\text{ptox} = 0.05$ under the alternative hypothesis)

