Illustrates how the joint event probabilities a, b, c and d at the end of the study relate. Namely, if we assign $a = 0.02$ then b, c and d can be determined by subtraction. Here we would get: $b = 0.54$, $c = 0.03$ and $d = 0.41$. For any value of a in $(0, 0.05)$ the other three terms are completely specified. In this design we are considering toxicity to be cumulative. We model the total chance of UT to occur with fraction f in the first interval (0, 8 weeks) and $1-f$ in the final 8 weeks. We have considered fractions $f = 0, 0.25, 0.5, 0.75$ and 1.0 , i.e. $f=0$ implies no toxicity in the first 8 weeks and $f = 1$ implies all toxicity occurs then. The final design is based on $f = \frac{1}{2}$.

P(UT)	1-p(UT)
a1	b1 p(PFS > 8) = 0.66
c1	d1 p(PFS < 8) = 0.34
ptox1	1 - ptox1 1 (ptox1 = ptox2 = 0.025 under the alternative with $f = \frac{1}{2}$) and
P(UT)	1-p(UT)
a2	b2 p(PFS > 16 PFS > 8) = 0.848
c2	d2 p(PFS < 16 PFS > 8) = 0.15
ptox2	1 - ptox2 1

The two tables above characterize the early stopping interval (0, 8 weeks) and final interval (8 weeks, 16 weeks). Numbers in the tables represent the alternative hypothesis. Patients in the initial cohort are represented by the top table (a1, b1, c1, d1) in the initial interval and those who are toxicity and progression free at 8 weeks, hence continue on study are represented by the second table (a2, b2, c2, d2) for their second 8 weeks. Patients recruited into the second cohort, if the study makes it past the first 8 week period, are evaluated only at 16 weeks and are represented by the very first table (a, b, c, d).

The chance of early stopping for excess toxicity, for futility, the chance of final declaration of excess toxicity, the power or type I error were all computed for each of the 4 conditions. Within each of these combinations, the fraction, f, of toxicity born within the first 8 weeks was varied in 5 steps from 0 to 1. We selected the number $f = \frac{1}{2}$ in the belief that toxicity is cumulative and this is the maximum fraction expected to occur in the first half of the trial. Design behavior for $f < \frac{1}{2}$ is ‘better’ than that for $f > \frac{1}{2}$, so is not reported here in detail.

The table below lists the various operating probabilities as functions of ‘a’ for each of the four conditions.

Key:

null = 0: PFS at 16 weeks = 0.35

null = 1: PFS at 16 weeks = 0.56

ntox = 0: Toxicity = 0.05

ntox = 1: Toxicity = 0.25

a: probability that PFS > 16 weeks and patient had UT

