1	1	0.06	0.2690	0.0483	0.5818	0.1006	1.0000
1	1	0.07	0.2690	0.0533	0.5770	0.1002	1.0000
1	1	0.08	0.2690	0.0587	0.5718	0.0997	1.0000
1	1	0.09	0.2690	0.0645	0.5664	0.0990	1.0000
1	1	0.10	0.2690	0.0706	0.5607	0.0981	1.0000
1	1	0.11	0.2690	0.0771	0.5548	0.0970	1.0000
1	1	0.12	0.2690	0.0840	0.5485	0.0957	1.0000
1	1	0.13	0.2690	0.0912	0.5419	0.0941	1.0000
1	1	0.14	0.2690	0.0988	0.5350	0.0923	1.0000
1	1	0.15	0.2690	0.1068	0.5278	0.0901	1.0000
1	1	0.16	0.2690	0.1152	0.5203	0.0877	1.0000
1	1	0.17	0.2690	0.1239	0.5126	0.0850	1.0000
1	1	0.18	0.2690	0.1330	0.5045	0.0819	1.0000

1	1	0.19	0.2690	0.1425	0.4962	0.0786	1.0000
1	1	0.20	0.2690	0.1522	0.4876	0.0749	1.0000
1	1	0.21	0.2690	0.1624	0.4787	0.0710	1.0000
1	1	0.22	0.2690	0.1728	0.4696	0.0668	1.0000
1	1	0.23	0.2690	0.1836	0.4602	0.0625	1.0000
1	1	0.24	0.2690	0.1947	0.4506	0.0580	1.0000
1	1	0.25	0.2690	0.2060	0.4408	0.0533	1.0000

Our analysis above is based on the assumption that toxicity is judged at 8 weeks and again at 16 weeks. In fact, the phase I portion of the study will not last beyond 4 weeks for each patient, so that the initial 3 patients, carried over from phase I, could become UT at 8 weeks. The tables above assume that the number of UTs at 8 weeks (not 4 weeks) is at most one. To account for this possibility, we re-computed the table assuming no restriction on the first 6 patients, but using only the early stopping rules for toxicity at 8 weeks. Thus the initial phase II cohort of all 17 patients in this re-computation are all treated alike. The results are shown in the next table. While the table above allows a smaller chance of toxicity than the actual trial, the table below allows a greater chance of toxicity in the initial phase II cohort. The main difference in the two computations is that the chance of early stopping for UT is about 9% higher under the re-computation conditions (35%) than it is under the top table (27%).

Operating characteristics of design with no restriction on the first 6 patients other than those tested at 8 or 16 weeks.

null	ntox	a	tox	fut	toxend	alpha	cksum
0	0	0.00	0.0082	0.4937	0.0114	0.2106	1.0000
0	0	0.01	0.0082	0.5103	0.0110	0.1862	1.0000
0	0	0.02	0.0082	0.5269	0.0106	0.1633	1.0000
0	0	0.03	0.0082	0.5434	0.0102	0.1421	1.0000
0	0	0.04	0.0082	0.5599	0.0098	0.1227	1.0000
0	0	0.05	0.0082	0.5762	0.0094	0.1049	1.0000

null	ntox	a	tox	fut	toxend	alpha	cksum
0	1	0.00	0.3591	0.2586	0.3197	0.0429	1.0000
0	1	0.01	0.3591	0.2700	0.3100	0.0393	1.0000

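### Unacceptable toxicity is defined at 8 weeks, but the 5% and 25% rates it is tested against are 16-week rates, and the decision rule in 8.1.2 names no window

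*Combined protocol and SAP*

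**What the plan says.** Wherever an endpoint or objective gives a window for UT, the window is 8 weeks. Section 3 lists "Unacceptable toxicity rate at 8 weeks" as a phase II secondary endpoint, and Section 8.1.1 defines it as "Composite of unacceptable toxicity at 8 weeks", to be reported as a proportion with a 95% confidence interval. The summary and Section 2 agree.

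Section 8.1.2 makes toxicity one of two phase II end-points and tests p(UT) above 0.25 against p(UT) below 0.05. Its interim toxicity rule begins "If 3/17 patients have UTs OR", and its final rule reads "If at least 14/34 patients are PF at 16 weeks AND less than 4/34 have UTs the null hypothesis will be rejected". PFS is given at 8 and 16 weeks in the hypotheses. UT has no time attached in the hypotheses or in either rule.

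Appendix 12.3 supplies a window, and it is a different one. There ptox, the quantity set to 0.05 or 0.25, is the probability of UT in 16 weeks. The probability of "UT in initial 8 week period" is f × ptox, with f set to 1/2 "in the belief that toxicity is cumulative and this is the maximum fraction expected to occur in the first half of the trial". The Appendix adds: "Patients recruited into the second cohort, if the study makes it past the first 8 week period, are evaluated only at 16 weeks". It also says: "Our analysis above is based on the assumption that toxicity is judged at 8 weeks and again at 16 weeks".

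**The concern.** The UT endpoint that carries a window is not the quantity behind the hypotheses, the cut points or the printed error rates. An analyst programming from Sections 3 and 8.1.1 would count UTs to week 8. One working from the Appendix would count to week 16. No passage reconciles the two.

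This matters because the UT count is half of the final decision rule and the trial's statistical safeguard against a toxic regimen. Under the Appendix's own assumption, a regimen at the unacceptable rate looks half as toxic at week 8 as at week 16. If the count is taken at week 16 instead, the decision is protected, but the reported endpoint and its interval describe something other than what was tested.

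**Working it through.** **Inputs.** From 8.1.2: suspend if 3 or more of 17 have UTs; pass toxicity at the end if 3 or fewer of 34 do; pass efficacy if 14 or more of 34 are progression-free (PF) at 16 weeks; interim futility if 8 or fewer of 17 are PF at 8 weeks. From 12.3: ptox 0.25 or 0.05; f = 1/2; PFS 0.66 at 8 weeks and 0.56 at 16 weeks; a = the probability of having a UT and also being PF at 16 weeks.

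**Step 1. Which window do the printed tables use?** With f = 1/2 the 8-week UT rates are 0.5 × 0.25 = 0.125 and 0.5 × 0.05 = 0.025. The early toxicity stop without the first-six restriction is P(X ≥ 3 | n = 17):

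| UT rate by week 8 | Computed | Printed in 12.3 |
|---|---|---|
| 0.125 | 0.3591 | 0.3591 |
| 0.025 | 0.0082 | 0.0082 |
| 0.25 | 0.836 | – |
| 0.05 | 0.050 | – |

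Conditioning on at most one UT in the first six patients gives 0.2690 and 0.0059, again as printed. So 0.25 and 0.05 are 16-week rates.

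**Step 2. Toxicity cuts alone, for a regimen with 25% UT by week 16.**

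- Counting to week 8 (rate 0.125), final cut alone: P(X ≤ 3 | 34, 0.125) = 0.371. The expected count is 34 × 0.125 = 4.25.
- Counting to week 8, interim and final cuts: the sum over u = 0, 1, 2 of P(U₁ = u) × P(U₂ ≤ 3 − u), with 17 patients per stage, is 0.1033 × 0.8457 + 0.2509 × 0.6409 + 0.2867 × 0.3542 = 0.350. With the first-six restriction it is 0.339 unconditionally and 0.406 given that the restriction is met.
- Counting to week 16 (rate 0.25), final cut alone: P(X ≤ 3 | 34, 0.25) = 0.017. The expected count is 34 × 0.25 = 8.5. Adding the interim cut also gives 0.017.

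**Step 3. Dependence on f.** The final cut alone, applied to 8-week UTs, passes 83.9% at f = 0.25, 37.1% at f = 0.5, 9.6% at f = 0.75 and 1.7% at f = 1. The Appendix regards 1/2 as the largest plausible f, so on its own belief the 8-week pass rate is not lower than this.

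**Step 4. Chance of declaring efficacy under the Appendix's joint model** (UT 0.25, PFS 0.66/0.56, P(PF at 16 | PF at 8) = 0.56/0.66 = 0.848; a patient counts as a success only if PF without a UT). This model reproduces the printed columns to four decimals in all nine rows checked from the first set of tables. The final count is then switched to 8-week UTs only:

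| First-six restriction | a | Printed type I error | 8-week count |
|---|---|---|---|
| Yes | 0 | 10.1% | 39.3% |
| Yes | 0.25 | 5.3% | 13.9% |
| No | 0 | 8.9% | 33.8% |
| No | 0.25 | 4.7% | 11.9% |

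Near independence of UT and PFS (a = 0.14), without the restriction, the 8-week count gives 26.1%.

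**A point on the comparator.** The printed values reproduce only if stage 1 UTs from weeks 0 to 8 are left out of the final count. Counting every UT to week 16, as the 4/34 rule reads, gives 3.6% (a = 0) to 2.2% (a = 0.25) in the restricted case.

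**The case against.** The strongest reply is that the decision window is already specified. Section 4.5 defines UT by type and grade with no 8-week limit and says the category will be used in the phase II statistical design. Section 8.1.2 sends the reader to Appendix 12.3, which judges toxicity at 8 and again at 16 weeks. The final rule pairs the UT count with PF at 16 weeks in one sentence. On this view the 8-week rate is a separate secondary summary, and Section 8.1.1 says its analyses are for estimation only.

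Much of this stands. The Appendix reading is the better one, and under it the final count does not have the problem in Step 2. A reader might infer that the plan, as specified, declares a 25%-UT regimen efficacious about a third of the time. The documents do not support that. It requires overriding the Appendix. Also, about a third is the pass rate of the toxicity cuts alone: efficacy must be met as well, and the result depends on the UT–PFS association and the first-six restriction. A calculation treating UT and PFS as independent and separable gives 31.5% against 1.5%, but it is not the Appendix's model.

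What does not stand is that the gap is harmless. Section 4.5 gives no assessment window for the count, 8.1.2 gives none, and every endpoint statement with a window says 8 weeks. The estimation-only remark sits beside an 8.1.2 rule that rejects a null hypothesis and declares the treatment efficacious partly on the UT count.

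**Conclusion.** The mismatch is real and lies in a final decision criterion. Its consequence depends on which window is applied.

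- **8-week endpoint used in the final rule:** the toxicity cuts pass a regimen with 25% UT by week 16 about 35% of the time instead of about 1.7%. The chance of declaring efficacy at PFS 0.56 is about 12% to 39%, against a stated 5% to 10%.
- **16-week window of the Appendix used:** the rule does not have this problem. The reported 8-week rate and its interval would centre on 12.5% for the same regimen, which cannot be read against 0.05 or 0.25.

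These figures assume f = 1/2 and take 25% as the rate by week 16. If 25% were the 8-week rate itself, the final cut would pass only 1.7%. The efficacy range also rests on the Appendix's joint model, with a running from 0 to 0.25.

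**What to change.** In 8.1.2, write the hypotheses as p(UT by 16 weeks), the interim rule as UTs by week 8, and the final rule as fewer than 4/34 with a UT by week 16. In Sections 3 and 8.1.1, add the cumulative 16-week UT rate with its confidence interval and name it as the quantity tested. Keep the 8-week rate as a descriptive secondary figure; it need not be removed.

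The cost is wording only. Sample size and cut points stay the same, and the Schedule of Events already continues adverse event monitoring every 4 weeks after the first two cycles. The reported 16-week rate will be higher than the 8-week rate. The Appendix tables should be re-run to match the cumulative count. With stage 1 UTs from weeks 0 to 8 included, power runs from 84.5% (a = 0) to 78.4% (a = 0.05), so it falls slightly below the stated 80% at the upper end of a.
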